##### **8.2.1.2 Sample Size Calculation in regard to $\beta_2$ - MG Reduction Ratio**

A previously conducted Theranova HDF study was used to obtain  $\beta_2$ -MG RR mean and SD

of 78.48 and 6.75; a higher estimate for SD of 14.28 is used to calculate sample size to account for a potential increase in variability based on a literature review of studies conducted in China. Based on a 1:1 randomization, with a sample size of 75 patients in the Theranova 400 group and 75 patients in the FX 800 group (total N = 150), a Wilcoxon Rank-Sum test  $\alpha$  with a 0.025 one-sided significance level will have 90% power to demonstrate non-inferiority of the Theranova 400 Dialyzer compared to the FX 800 Dialyzer as assessed by  $\beta$ 2-MG RR with a non-inferiority margin of 10% (i.e. 7.848).

### **8.2.1.3 Sample Size for this Study**

Consequently, in order to demonstrate non-inferiority between Theranova 400 and FX 800 in both primary endpoints, a sample size of 129 patients in the Theranova 400 group and 129 patients in the FX800 group is required to guarantee 90% power for the analysis of  $\lambda$  FLC and > 90% power for the analyses of  $\beta$ 2-MG. To allow for 5% of patients to drop out or be excluded from the Per-protocol population as a result of patient classification, a total of 272 patients will be randomized 1:1 to treatment with the Theranova 400 Dialyzer (136 patients) or treatment with the FX 800 Dialyzer (136 patients).

### **8.2.2 Sample Size for each Disease and Justification**

This clinical study does not involve the determination of sample size for each disease.

### **8.3 Significance Level and Power of Clinical Study**

A 0.025 one-sided significance level and a power of 90% were used in planning this study.

### **8.4 Expected Dropout Rate**

It is estimated that the expected ratio of cases with dropout or serious protocol violations is about 5%.

This ratio refers to the proportion of patients who ultimately cannot be evaluated for primary efficacy on the per-protocol analysis set. This part of patients are those who have been dropped out or have serious protocol violation (affecting the evaluation of primary endpoints) after confirmed by the principal investigator (PI).

### **8.5 Eligibility/Fail Criteria for Clinical Study Results**

Let  $\mu_T$  denote the Theranova 400 treatment mean and let  $\mu_R$  denote the FX 800 treatment mean. The statistical hypothesis of the study can be written as:

$$H_0: \mu_T - \mu_R \leq -\delta$$

$$H_a: \mu_T - \mu_R > -\delta$$

When evaluating the primary endpoint of  $\lambda$  FLC, the non-inferiority margin is -3.783 (10% of assumed mean RR of 37.83%). When evaluating the primary endpoint of  $\beta$ 2-MG RR, the non-inferiority margin is -7.848 (10% of assumed mean reduction ratio of 78.48%). When the non-inferiority of the two primary endpoints of  $\lambda$  FLC and  $\beta$ 2-MG RRs are both established, the non-inferiority of this study is established.

### **8.6 Criteria for Discontinuation of Study Based on Statistical Reasons and Justification**

---

No statistical stopping rules are stipulated for this study.

## **8.7 Statistical Methods of all Data, together with Processing of Missing, Unused or Erroneous data (including midway exit and withdrawal) and Unreasonable Data**

### **8.7.1 Data Statistical Analysis**

#### **8.7.1.1 Analysis of Primary Endpoints**

For the  $\lambda$  FLC and  $\beta2$ -MG RR endpoints, let  $\mu_T$  denote the TheraNova 400 treatment mean and let  $\mu_R$  denote the FX 800 treatment mean. Then the null hypothesis to demonstrate non-inferiority using a 10% margin for  $\lambda$  FLC RR can be expressed as:  $H_0: \mu_T - \mu_R \leq -3.783$ . The alternative hypothesis is expressed as:  $H_a: \mu_T - \mu_R > -3.783$ . A t-test will be utilized to generate a two-sided 95% confidence interval (CI) for the difference in means ( $\mu_T - \mu_R$ ). If the lower bound of the CI is  $> -3.783$ , then non-inferiority between the TheraNova 400 and FX 800 treatment group can be demonstrated for  $\lambda$  FLC RR. If the lower bound of the CI  $> 0$ , then superiority of TheraNova 400 treatment over FX 800 treatment can be concluded.

Equivalently the null hypothesis to demonstrate non-inferiority using a 10% margin for  $\beta2$ -MG RR can be expressed as  $H_0: \mu_T - \mu_R \leq -7.848$ . The alternative hypothesis is expressed as:  $\mu_T - \mu_R > -7.848$ . A t-test will be utilized to generate a two-sided 95% confidence interval (CI) for the difference in means ( $\mu_T - \mu_R$ ). If the lower bound of the CI is  $> -7.848$ , then non-inferiority between the TheraNova 400 and FX 800 treatment group can be demonstrated for  $\beta2$ -microglobulin RR. If the lower bound of the CI  $> 0$ , then superiority of TheraNova 400 treatment over FX 800 treatment can be concluded.

Two sensitivity analysis will be conducted for both endpoints:

1. An ANOVA model with fixed effects for treatment group and study site to evaluate differences between the treatment groups will be analyzed and corresponding two-sided 95% CIs derived.

A non-parametric method: Wilcoxon Rank-Sum Test will be used to analyze the primary endpoints.

In case the assumption of a normal distribution is not justified, RRs can be log transformed in order for the measurements to follow a normal distribution. If, after transformation, measurements do still not follow a normal distribution, above statistical analyses methods will be replaced with their non-parametric equivalents. The Wilcoxon Rank-Sum Test will be used in place of the t-test while the Kruskal Wallis test will be used in place of the ANOVA.

#### **8.7.1.2 Analysis of Secondary Endpoints**

Secondary endpoints will be evaluated as follows:

A t-test or Wilcoxon Rank-Sum test, as applicable, will be used to evaluate differences between treatment groups in  $Kt/V_{urea}$  and URR.

A t-test or Wilcoxon Rank-Sum test, as applicable, will be used to evaluate differences between treatment groups for the RRs of  $\alpha1$ -MG, YKL-40, CFD, myoglobin and  $\kappa$  FLC obtained at the mid-week treatment day dialysis session.

### 8.7.1.3 Analysis of Safety Endpoints

Safety endpoints will be evaluated as follows:

1. The summary of AEs will include AEs that occur on the day of or after the study treatment. Pre-treatment AEs including AEs reported at Screening and Randomization will be recorded in the eCRF but will not be summarized in the safety tables. Adverse events will be mapped to a Primary System Organ Class (SOC) and Preferred Term (PT) according to Medical Dictionary for Regulatory Activities (MedDRA) and summarized descriptively by SOC, PT and treatment group. Treatment group comparability in the incidence of AEs will be evaluated using Fisher's exact test. An overview (overall) summary table of all AEs will be generated that includes the total number of AEs, number and percentage of patients with at least one AE, number and percentage of patients with at least one SAE, number and percentage of patients with at least one severe AE, number and percentage of patients with at least one AE probably associated with study treatment, number and percentage of patients with an AE leading to study discontinuation and number and percentage of patients with an AE leading to death. This summary will be presented by treatment group and combining both groups (Total). In addition, two separate AE summary tables will be provided, one for analysis by severity and relationship to the study dialyzer, and the other will provide a separate AE summary table for SAEs and AEs that led to withdrawal from the study.
2. Device deficiencies (DD) will be summarized descriptively.
3. Serum chemistry, hematology assessments, liver function, patient vital signs, and CRP will be summarized descriptively per measurement time point using n, mean, median, standard deviation, minimum, and maximum.

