## **8.11 Interim Analysis**

A blinded interim analysis for sample size re-estimation will be conducted when approximately 50% of patients complete theirmid-week treatment day dialysis session and corresponding  $\lambda$  FLC and  $\beta$ 2-MG RRs are available.

This interim analysis allows for modifying the sample size while the study is ongoing and is based on a blinded estimate of the variance. The one-sample estimator which will be calculated

---

from the pooled data maintains trial integrity, shows good performance and is therefore recommended for application [22].

The data utilized during the interim analysis will be based on the FAS and statistics will be limited to the calculated one-sample variance estimator (not split by treatment group) of the  $\lambda$  FLC and  $\beta 2$ -MG RRs measured at the mid-week treatment day dialysis session. For sample size re-estimation, for each primary endpoint, the same sample size calculation as outlined in Section 8.2 will be carried out using the one-sample variance estimator which is based on the pooled variance (across both treatment groups) of the RRs as observed in the patients included in the interim analysis. In case the re-estimation for the sample size of  $\lambda$  FLC or  $\beta 2$ -MG yields a patient number  $> 272$  (including 5% drop out), the sample size of the study will be increased to this re-calculated number but will not exceed 350. In case the sample size reassessment for  $\lambda$  FLC or  $\beta 2$ -MG yields a patient number  $\leq 272$  (including 5% drop out), the sample size of the study will not be adjusted and the original sample size of 272 will be maintained. Due to this blinded and pooled (non-treatment group based) approach in re-estimation of the sample size and the absence of early stopping for futility and efficacy, no alpha adjustment is required for the final analysis.

This interim analysis does not involve comparison of efficacy between groups, and will be performed by the sponsor or a Contract Research Organization (CRO) or a third party authorized by the sponsor. The details will be described in the Statistical Analysis Plan.

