### 3.1 General Description

A randomized, controlled, open-label, parallel, multicenter study.

The study population consists of patients with kidney failure on a stable HD and/or HDF prescription. A sufficient number of patients will be enrolled to ensure 272 patients are randomized 1:1 to either Theranova 400 (136 patients) or FX 800 (136 patients). All patients will receive one (1) session of mid-week therapy with either Theranova 400 or FX 800. A follow-up session is scheduled at the next treatment (end-week) session, but prior to

treatment commencement (See Figure 1).

Figure 1: Clinical Trial Design Flow

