### **6.3 Safety Set (SS)**

Includes all enrolled patients (ICF signed) that have been treated. Patient assignment will be based on actual treatment received.

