### **7.5 Statistical Tests**

Unless specified, all statistical tests will be performed at a significance level of 5% with two-sided 95% confidence interval (CI).

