### 8.2 Multiple Comparisons / Multiplicity

The two primary endpoints will be tested simultaneously. Only when both primary endpoints pass is the study declared successful. Therefore, no multiplicity adjustment are necessary for this portion. Hierarchical structure will be used for the testing for both non-inferiority and superiority. Superiority will only be tested if non-inferiority passes.

There are no other multiplicity adjustments are made for the study. The secondary endpoint is not assigned to alpha, so it not refers to alpha adjustment. All secondary endpoints, all p values are descriptive in nature only.

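### Comparability of adverse-event incidence is assigned to Fisher's exact test, which can show a difference but not comparability, and the visible text names no incidence difference with an interval

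*Protocol*

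**What the plan says.** Protocol 8.7.1.3 states: "Treatment group comparability in the incidence of AEs will be evaluated using" Fisher's exact test. The Statistical Analysis part of the synopsis and SAP 18.2 repeat the sentence. The rest of 8.7.1.3 and SAP 18.2.1 to 18.2.9 call for counts, percentages, summaries by system organ class and preferred term, and listings, by arm.

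Three other SAP sections bear on how that test would be read:

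- SAP 7.5 sets the default that, unless specified, "all statistical tests will be performed at a significance level of 5% with two-sided 95% confidence interval (CI".
- SAP 8.2 says "All secondary endpoints, all p values are descriptive in nature only". The sentence before it is also about the secondary endpoint. AEs are listed as safety assessments (Protocol 7.1.7), not among the secondary endpoints (Protocol 7.1.6.1).
- SAP 9 gives the table templates priority over the SAP text where the two differ. The templates are not part of the documents available.

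The safety set "Includes all enrolled patients (ICF signed) that have been treated", analysed by the treatment actually received. The planned size is "272 patients are randomized 1:1 to either Theranova 400 (136 patients) or FX 800 (136 patients".

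**The concern.** Fisher's test starts from equal incidence and asks whether the data contradict it. A small p-value is evidence of a difference. A large one may mean that the arms are alike, or only that the sample is too small to tell. It therefore cannot answer the question the sentence sets.

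The choice of word stands out. For secondary endpoints (Protocol 8.7.1.2) and baseline variables (8.7.1.4), the protocol describes its tests as looking for differences. Only for AEs is a difference test said to evaluate comparability. For efficacy the same plan avoids the problem: it sets a margin and reads the lower confidence bound against it (Protocol 8.5 and 8.7.1.1).

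What is at stake is the safety statement. Protocol 3.2 says AEs are monitored to evaluate the safety of Theranova 400 as well as its efficacy, and Protocol 4 says the report will support registration. If the safety section rests on Fisher p-values, an excess on the new dialyzer that the data cannot exclude may go unremarked.

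**Working it through.** **1. The plan's own figure.** The documents state no power and no assumed rate for AEs. Sample size rests on the two reduction ratios. The larger requirement is for λ FLC (margin 3.783, SD 9.09, one-sided 0.025, 90% power; Protocol 8.2.1.1 and 8.3). The t-based n is 123 per arm. Dividing by the Wilcoxon efficiency 3/π gives 123 × π/3 = 128.8, so 129. Allowing 5% loss, 129 / 0.95 = 135.8, so 136. The stated 129 and 136 are reproduced, and AE incidence plays no part in them.

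**2. Power of the AE test.** Inputs: 136 per arm (SAP 3.1), assuming every randomized patient is treated; two-sided 5% level (SAP 7.5). The incidences are assumptions. Exact power is the sum, over all pairs of counts (i, j), of Bin(i; 136, p1) × Bin(j; 136, p2) wherever the two-sided Fisher p is at most 0.05.

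| Assumed incidences | Power | Missed |
|---|---|---|
| 1% vs 2% | 1.7% | 98.3% |
| 2% vs 5% | 15.7% | 84.3% |
| 5% vs 10% | 26.3% | 73.7% |
| 20% vs 30% | 42.4% | 57.6% |
| 10% vs 20% | 58.5% | 41.5% |
| 15% vs 30% | 81.4% | 18.6% |
| 20% vs 40% | 94.0% | 6.0% |

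For 5% vs 10%, power is 24.5% at 129 per arm. Under the interim rule, "the sample size of the study will be increased to this re-calculated number but will not exceed 350"; at that cap (175 per arm) power is 35.0%. An uncorrected normal approximation at 136 per arm gives 34.6%, so the exact figure is the one to use for a Fisher test. About 435 per arm (uncorrected) or 474 (continuity-corrected) would be needed for 80% power.

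**3. What an interval adds.** Take 14/136 (10.29%) on Theranova 400 and 7/136 (5.15%) on FX 800. Fisher p = 0.17. The difference is 10.29 − 5.15 = 5.15 points (from unrounded values). The Wilson limits are 6.23% to 16.54% and 2.52% to 10.24%. Newcombe's method combines them:

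- lower limit: 5.15 − √[(10.29 − 6.23)² + (10.24 − 5.15)²] = 5.15 − 6.52 = −1.4
- upper limit: 5.15 + √[(16.54 − 10.29)² + (5.15 − 2.52)²] = 5.15 + 6.78 = 11.9

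The p-value is unremarkable, yet the data are compatible with an excess of nearly 12 points.

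A sharper case is 17/136 vs 7/136 (12.5% vs 5.1%). Fisher p = 0.052, which is not significant, while the Newcombe interval is 0.5 to 14.5 points and lies wholly above zero.

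**The case against.** The strongest reply is that no decision rule exists to be wrong. A reader might infer that p > 0.05 will be reported as comparable safety. The documents do not say so: that reading rests on one word, and no pass or fail criterion is attached to AEs. Study success depends only on the two reduction ratios (Protocol 8.5, SAP 8.2), and safety appears in no primary or secondary objective. This stands, and it limits the point to how safety is reported.

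Second, SAP 7.5 pairs its 5% level with a two-sided 95% CI, which could be read as already attaching an interval to the AE test. It is a generic default: it names no estimand, no method for proportions and no AE table. It weakens a claim that intervals are absent from the plan, but does not supply one for AE incidence.

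Third, the templates override the SAP text and may contain a difference or an interval. That cannot be checked, so the point is about the visible text only.

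Fourth, AE reporting is already largely descriptive, and an imbalance such as 14 vs 7 would show in the tables. The closing sentence of SAP 8.2 might also be read to cover Fisher p-values. But it is worded for secondary endpoints, and counts alone do not tell the reader how large an excess remains possible.

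Fifth, the power figures depend on assumed rates. This is correct: power is adequate for a large difference in a common event and poor for uncommon ones. Low power for uncommon AEs is to be expected in a one-session trial sized on reduction ratios, and is not itself a fault.

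Finally, an interval without a margin gives no criterion for comparability. True, but it shows what the data can and cannot exclude, which the p-value does not.

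**Conclusion.** The point holds as one of method and wording. In three places the plan assigns comparability of AE incidence to a test that cannot establish it, and the visible text names no between-arm difference with an interval. No primary conclusion, error rate or patient number changes. The exposure is a misleading safety statement.

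The size is illustrative. A doubling from 5% to 10% would be missed about three times in four at 136 per arm, but those rates are assumed, and across the doublings examined the miss rate runs from about 98% (1% vs 2%) to 6% (20% vs 40%). The documents do not support the stronger claim that the plan declares safety comparable whenever p exceeds 0.05. The change is worth making because it is cheap and uses data already being collected.

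**What to change.** In the synopsis, Protocol 8.7.1.3 and SAP 18.2, replace the comparability sentence with the following:

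- Report the difference in incidence (Theranova 400 minus FX 800) with a two-sided 95% CI, for example by Newcombe's method. Do this for patients with any TEAE, any SAE, any treatment-related AE and any procedure-related AE, and for preferred terms at or above the 5% threshold that SAP 18.2.4 already uses.
- Label any retained Fisher p-values as descriptive tests of difference, and state that a non-significant p-value does not show comparable safety.
- Base any remark on comparability on the interval, and say that no safety margin was set.

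Carry the same change into the AE table templates, since SAP 9 gives them priority.

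The cost is wording in the two documents and one extra column in the AE tables, with no new data or patients. The downside is that the safety statement will read less favourably when intervals are wide.

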### 8.7.1.4 Other Assessments

Continuous and categorical demographic and baseline characteristics will be summarized by treatment groups. A t-test or Wilcoxon Rank-Sum test, as applicable, will be used to assess differences between treatment groups in continuous variables and Fisher's exact test will be used to assess differences between treatment groups in categorical variables.

## 8.7.2. Processing of Missing, Unused or Erroneous Data (including midway exit and withdrawal) and Unreasonable Data

All missing, unused or erroneous data (including midway exit and withdrawal) and unreasonable data will be discussed and finalized determined by the investigators and biostatisticians during the data review phase. The basic statistical principles of these data processing are as follows:

- (1) Describe the details of each dropout case, and compare the dropout between the test group and the control group by using  $\chi^2$  or Fisher's exact probability method;
- (2) Missing data at baseline will not be imputed;
- (3) Missing values of primary efficacy endpoints of  $\lambda$  FLC and  $\beta2$ -MG RRs will not be imputed.
- (4) Missing values of the secondary efficacy endpoints and safety endpoints will not be filled;

---

- (5) Erroneous and unreasonable data will be processed as missing values;
- (6) Sensitivity analysis will be performed for the primary efficacy endpoints using the full analysis set (FAS), after utilize last observation carried forward (LOCF) to impute the missing values of the  $\lambda$  FLC and  $\beta$ 2-MG RRs.

## **8.8 Procedures for Reporting Deviations from the Original Statistical Program**

Generally, only the statistical analysis content stipulated in advance in the statistical analysis plan can be presented in the clinical study report of this study. The additional statistical analysis due to various uncertain reasons is only for exploratory purpose.

Any deviations from the statistical analysis plan will be documented and described with details.

## **8.9 Criteria for Selection of Patients Included in the Analysis and Justification**

- (1) Intention-to-treat FAS: Includes all randomized patients. Patient assignment will be based on the treatment randomized.
- (2) Per-Protocol Set (PPS): Is a subset of the FAS and meets the following requirements: Patients were randomized to the respective treatment at themid-week treatment day dialysis session and did not have any major protocol deviations that could affect the assessment of the primary endpoint when dividing the patient population. Major protocol deviations when dividing the patient population are defined as follows: :
  - 1) The actual QB of the patient is  $< 220$  mL/minute for a duration of more than 30 min or for a total duration of  $> 60$  minute at themid-week treatment day dialysis session; patients in control group who actually do not achieve at least 16 L convective volume (including UF)
  - 2) The actual dialysis time of the patient is  $< 210$  minute at themid-week treatment day dialysis session.
- (3) Safety analysis set (SS): Includes all enrolled patients (ICF signed) that have been treated. Patient assignment will be based on actual treatment received.

The analysis of the primary endpoint will be based on the PPS, with a supportive analysis of the primary endpoint based on the FAS. Unless otherwise specified, the remaining analyses will be based on the FAS. All safety related analyses will be based on the SS.

## **8.10 Exclusion of Special Information when Verifying Assumptions and Justification, if applicable**

Not applicable.

## **8.11 Interim Analysis**

A blinded interim analysis for sample size re-estimation will be conducted when approximately 50% of patients complete theirmid-week treatment day dialysis session and corresponding  $\lambda$  FLC and  $\beta$ 2-MG RRs are available.

This interim analysis allows for modifying the sample size while the study is ongoing and is based on a blinded estimate of the variance. The one-sample estimator which will be calculated

---

from the pooled data maintains trial integrity, shows good performance and is therefore recommended for application [22].

The data utilized during the interim analysis will be based on the FAS and statistics will be limited to the calculated one-sample variance estimator (not split by treatment group) of the  $\lambda$  FLC and  $\beta 2$ -MG RRs measured at the mid-week treatment day dialysis session. For sample size re-estimation, for each primary endpoint, the same sample size calculation as outlined in Section 8.2 will be carried out using the one-sample variance estimator which is based on the pooled variance (across both treatment groups) of the RRs as observed in the patients included in the interim analysis. In case the re-estimation for the sample size of  $\lambda$  FLC or  $\beta 2$ -MG yields a patient number  $> 272$  (including 5% drop out), the sample size of the study will be increased to this re-calculated number but will not exceed 350. In case the sample size reassessment for  $\lambda$  FLC or  $\beta 2$ -MG yields a patient number  $\leq 272$  (including 5% drop out), the sample size of the study will not be adjusted and the original sample size of 272 will be maintained. Due to this blinded and pooled (non-treatment group based) approach in re-estimation of the sample size and the absence of early stopping for futility and efficacy, no alpha adjustment is required for the final analysis.

This interim analysis does not involve comparison of efficacy between groups, and will be performed by the sponsor or a Contract Research Organization (CRO) or a third party authorized by the sponsor. The details will be described in the Statistical Analysis Plan.

